Baclofen is a GABA receptor agonist that is FDA-approved to treat spasticity. Baclofen has an established clinical safety profile, as well as evidence to support its use in addictions, primarily with alcohol use disorders. Our preclinical evidence suggests baclofen, in combination with buprenorphine, increases the analgesic effects of buprenorphine in rodents. Using these medications together may offer an important novel strategy to increase retention in treatment and adherence to buprenorphine while preserving the safety profile of a partial opioid agonist, particularly among patients with a chronic pain condition who may be more likely to abuse illicit opioids. However, data for this approach in humans is lacking and initial evidence is needed to assess the analgesic interaction, safety, acceptability and feasibility of using buprenorphine and baclofen in humans before conducting a larger clinical trial to examine efficacy in patients.

Brief purpose of the study

The purpose of the study is to determine if baclofen will enhance buprenorphine analgesia for acute pain in healthy volunteers (non-opioid users). We will first recruit 30 healthy volunteers (Group 1) who will be administered either 4mg of Buprenophine, 5 mg of Baclofen, or 10 mg of Baclofen in order to test the effects of the drugs on pain separately.

Then, we will recruit another 60 healthy volunteers (non-opioid users; Group 2) and randomize them to either placebo, 5mg or 10 mg of baclofen (1 dose) in combination with 4 mg of buprenorphine to examine analgesia in acute pain tasks.

Measurement occurrence

Data Collection Instrument	Session 1	Session 2
Informed consent	✓	
Screening questions (survey)	✓	
Vital signs: blood pressure, heart rate, temperature, neck circumference, height/weight	✓	✓
Blood draw	✓	✓
Pregnancy test		✓
Urine drug screen		✓
Demographics questionnaire (survey)		✓
Profile of Mood States Questionnaire (POMS) (survey)	✓	✓
QST: Cold pressor task	✓	
QST: Heat pain task	✓	✓
QST: Cold pain task	✓	✓
QST: Mechanical pressure pain task	✓	✓
QST: Conditioned pain modulation task	✓	✓
QST: Pinprick pressure pain task	✓	✓
26-item Visual Analog Scale (VAS) (survey)		✓
Drug Effects Questionnaire-5 (survey)		✓
Opioid symptom checklist		✓

Accessing the shared drive

1. Click on the home button at the bottom left hand of the computer
2. Go to “Computer”
3. Click on “PBN.” Enter your blazer ID and password if necessary
4. Click on “[name]-Lab”

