Participants will then complete the POMS and the Opioid Symptom Checklist prior to taking the study drug. These questionnaires will be entered directly into REDCap by the participant as a survey. Then, alert the nurse that you are ready for them to give the pt the study drug. Note that it can sometimes take up to an hour for the nurse to retrieve the drug from the pharmacy, so you may have to wait a little bit.

Then participants will be administered the study drug:

- First cohort (n=30): Randomized to either 5 mg of baclofen, 10 mg baclofen ,or 300 mcg of buprenorphine (n=10 per group). **All participants in this cohort will receive one dose of one single drug compound.**
- Second cohort (n=60): Randomized to 300 mcg of buprenorphine, and either: placebo, 5 mg of baclofen, or 10 mg of baclofen (n=20 per group). **All participants in this cohort will receive a combination of drug compounds.**

Participants will be instructed to take the drug(s) orally (baclofen) or buccally as a film (buprenorphine). Following the administration of the study drug, all study procedures are identical for all groups and cohorts.

Visit timeline

The visit timeline for session 2 is as follows (represented below in 15-minute segments):

Group 1 (single compound)

-1	0	15	30	45	1 hr	15	30	45	2 hrs	15	30	45	3 hrs
Vitals, surveys, OSC	Adm drug OSC	Vitals	Vitals, blood draw #1, surveys	...	Vitals OSC	...	QST	...	Vitals, OSC	...	Blood draw #2	...	Vitals, OSC
Begin 3 hour post-dose observation End observation													

Group 2 (duo compound)

0	15	30	45	1 hr	15	30	45	2 hrs	15	30	45	3 hrs	15	30	45	4 hrs
Vitals Surveys OSC	Adm Bup OSC	Vitals	Adm Bac	...	Vitals, blood collection	Surveys	Vitals OSC	...	QST	...	Vitals OSC	Vitals OSC
Begin 3 hour post-dose observation End observation																

Participants are asked to stay for a 3-hour observation period post-drug administration as that is the amount of time it typically takes for the drug(s) to leave their system. This observation period will allow us to monitor the side effects of the medications while it is still in their system. During the observation period, participants' vital

signs will be taken periodically to monitor drug side effects. We will also administer the Opioid Symptom Checklist at various timepoints to quantify the drug's effects.

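### The protocol gives two nominal buprenorphine doses, 4 mg and 300 mcg, for every arm that receives buprenorphine, and nothing in the text reconciles them

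*Protocol*

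**What the plan says.** The protocol describes the treatment arms twice.

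- **Brief purpose of the study.** Group 1 comprises volunteers "who will be administered either 4mg of Buprenophine, 5 mg of Baclofen, or 10 mg of Baclofen". Group 2 receives placebo or one of two baclofen doses "in combination with 4 mg of buprenorphine to examine analgesia in acute pain tasks". No route or formulation is given here.
- **Study session 2, drug administration step.** The first cohort is "Randomized to either 5 mg of baclofen, 10 mg baclofen ,or 300 mcg of buprenorphine (n=10 per group"). The second is "Randomized to 300 mcg of buprenorphine, and either: placebo, 5 mg of baclofen, or 10 mg of baclofen (n=20 per group"). The text that follows says baclofen is taken by mouth and buprenorphine as a buccal film.

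The SAP names three groups: placebo, baclofen 5 mg and baclofen 10 mg. These labels match the three Group 2 arms. The SAP mentions buprenorphine only in the trial title and gives no dose for it.

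**The concern.** The trial asks whether baclofen enhances buprenorphine analgesia, so the buprenorphine dose is part of the question. In Group 2 it is the treatment common to all three arms. In Group 1 it is one of the single-compound arms, against which the combination would naturally be read.

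If the dose is uncertain, three things suffer:

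- **Safety.** Participants are healthy volunteers who do not use opioids, and the introduction names safety as one of the things to be learned. An adverse event cannot be tied to an exposure that the protocol states in two ways.
- **Interpretation.** The SAP plans descriptive summaries only. A mean and standard deviation per group say little if the treatment given to that group is not identified.
- **Reuse.** The introduction presents this study as groundwork for a larger trial in patients. That trial cannot build on a dose that readers cannot determine.

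The document is also a working manual for study staff. Someone consulting one section could come away with a different dose from someone consulting the other.

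**Working it through.** **Step 1. Do the two sections describe the same arms?**

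| Item | Brief purpose of the study | Study session 2, administration |
|---|---|---|
| First cohort size | 30 | 30 (10 per arm) |
| Second cohort size | 60 | 60 (20 per arm) |
| Baclofen doses | 5 mg, 10 mg | 5 mg, 10 mg |
| First cohort arms | buprenorphine alone, or one of two baclofen doses alone | same |
| Second cohort arms | buprenorphine with placebo or one of two baclofen doses | same |
| Buprenorphine dose, first cohort | 4 mg | 300 mcg |
| Buprenorphine dose, second cohort | 4 mg | 300 mcg |
| Buprenorphine route and form | not stated | buccal film |

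The cohort sizes reproduce from the arm sizes: 3 × 10 = 30 and 3 × 20 = 60. Arms and baclofen doses match, so both sections describe the same six arms. Apart from the route, which only one section gives, the buprenorphine dose is the only row that disagrees.

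**Step 2. How large is the disagreement?**

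4 mg × 1000 = 4000 mcg. Then 4000 / 300 = 13.3, or the other way round 300 / 4000 = 7.5%. This is a ratio of nominal doses. The purpose section gives no route, so systemic exposure cannot be compared from the documents.

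**Step 3. Who is affected?**

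- Arms: 1 in the first cohort + 3 in the second = 4 of 6.
- Participants: 10 + (3 × 20) = 70 of 30 + 60 = 90, and 70 / 90 = 78%.

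**Step 4. Could it be a single typing slip, or is it resolved elsewhere?**

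Each figure appears twice, once per cohort, within its own section, and the units differ as well as the numbers. One mistyped value would not produce that pattern. The protocol carries one date (April 11, 2022), both figures stand in its current text, and no statement of equivalence or of a change connects them. The SAP is silent on dose.

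The exclusion criteria list sensitivity to naloxone, but the administration text does not mention naloxone. That does not settle the dose, but it is a further reason to have the formulation stated.

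**The case against.** The strongest reply is that the two sections do different jobs. One is a short statement of purpose; the other is the operating step, with dose, route, form and arm sizes. The drug is dispensed on a prescription sent to the investigational pharmacy before the visit, and a nurse collects it. Research staff are not told to take a dose from the purpose section. This stands as far as it goes: a dispensing error is possible rather than certain. It does not show which figure is correct, because the order form's content is not in the text available.

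The following qualifications also stand:

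- The available copy lacks a figure beside the session 2 paperwork list and the consent pages, either of which might state a dose. The claim is therefore limited to the visible text.
- Calling buprenorphine the background treatment fits Group 2 only. In Group 1 it is a test arm.
- Under either figure buprenorphine is constant across the three Group 2 arms, so the conflict alone does not confound a contrast between baclofen doses. The SAP makes no such comparison in any case.
- Nothing in the documents suggests that the dose changed during the study. That possibility belongs in the remedy only as a condition.
- The SAP is written in the past tense, so the remaining problem is probably one of record and reporting. That makes a traceable statement of the dose given more necessary, not less.

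None of these removes the contradiction.

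**Conclusion.** The concern holds. The protocol states two incompatible nominal buprenorphine doses, 13.3-fold apart, for each of the four arms that receive the drug. This is an internal contradiction in current text, not a criticism of a design decision. It must be fixed, because the dose defines the treatment being studied and the exposure of the volunteers.

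The conclusion assumes only that the two sections describe the same arms, which the matching cohort sizes and baclofen doses support, and that the planned numbers are those stated. It makes no claim about which dose was intended, approved or given, and none about the ratio of systemic exposures.

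**What to change.** 1. Reconcile the purpose section and the session 2 administration step so that both state one buprenorphine dose, formulation and route: those approved by the IRB and dispensed. Check them against the prescription orders and the investigational pharmacy's records.
2. State that treatment in the SAP, either in the arm labels or in one sentence saying what all three groups received alongside placebo or baclofen.
3. If the records show that the dose changed, say from which participant, and report results by dose received. If they show no change, say so.

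The cost is a check of dispensing records for the participants who received buprenorphine (70 as planned) and a wording correction in two documents. No new data are needed. Unless the records show more than one dose, no summary has to be rerun.

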If the participant reports any severe symptoms, or if their BP/HR readings become out of range, notify a CRU nurse immediately. You may also have to call the study doctor [name] ([contact]). It is a good idea to alert the PIs as well. If the participant is experiencing intense symptoms, you may have to skip the QST tasks. However, try to complete all study procedures if possible.

The QST tasks will be administered 1.5 hours post-drug administration.

Following the pain tasks, participants will complete a second 14 cc blood draw at around 145-155 minutes post-drug administration.

Pain tasks (QST)

The following Quantitative Sensory Testing (QST) tasks will then be administered by the research assistant at **1.5 hours post-drug administration** to allow for maximum drug efficacy:

Stimulus modality	Area of body	Tissue stimulated	QST response measures
Thermal (contact heat) Heat pain	Forearm	Cutaneous	
 • Pain threshold • Pain tolerance • Suprathreshold pain responses • Temporal summation of pain
Pinprick pressure pain	Middle phalange Trapezius	Cutaneous Myofascial	
 • Pain threshold • Pain tolerance • Suprathreshold pain responses • Temporal summation of pain
Mechanical (pressure) Pressure pain	Forearm Trapezius	Cutaneous Myofascial	
 • Pain threshold • Pain tolerance • Suprathreshold pain responses • Temporal summation of pain
Conditioned pain modulation Combined pressure and cold pain	Forearm Trapezius	Cutaneous Myofascial	
 • Cold immersion as the conditioning stimulus, and pressure contact as the test stimulus
Thermal (immersion cold) Cold pain	Hand	Cutaneous	
 • Pain threshold • Pain tolerance • Suprathreshold pain responses

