Combined Pressure and Cold Pain (CPM). The participant's hand will be immersed into cold water (8, 6, or 4 degrees C as designated by results from the initial cold pain task). After 30 seconds, the participant will rate the intensity of the pain from 0-100 (0 = no pain, 100 = most pain imaginable). They will keep their hand in the cold water for another 30 seconds, totaling 60 seconds of immersion in the cold water bath. Then, the pressure pain test will immediately be repeated on the opposite side of the body, and participants will again be asked to indicate the moment when they first feel pain due to the pressure stimulation by pressing a button. This task will be done 4 times in total (2 times on each body site). Just like before, the participant can stop any of these procedures at any time.

Cold Pressor Task. Following the CPM task, participants will complete the cold pressor task. They will be asked to put their dominant hand in the water at their specified temperature (i.e., 8, 6, or 4 degrees C) for as long as possible. Unbeknownst to participants, the maximum permitted immersion time will be five minutes – it is important that you do not tell them how long they will be keeping their hand in for. They will rate the intensity of the pain experienced using the 0-100 numeric rating scale at 30 second intervals and again immediately prior to hand removal. Time to removal of hand from the cold water will be used as a measure of cold pain tolerance. Participants will be told they can discontinue at any time they choose.

Questionnaires

Participants will complete the following questionnaires (in a REDCap survey format, participant enters data directly into REDCap) at 30-45 minutes post-drug administration:

- **Abbreviated Profile of Mood States Questionnaire (POMS):** This 36-item survey contains a series of descriptive words/statements that describe feelings people have. Participants are asked to self-report their current mood using a 5-point Likert scale. This survey takes approx. 5 minutes to administer.
- **26-item Visual Analog Scale (VAS):** A 26-item scale that measures subjective and physiological effects of a medication using mood states, as well as questions about the medication dose. This survey takes approx. 5 minutes to administer.
- **Drug Effects Questionnaire-5:** A 5-item questionnaire assessing drug effects. This survey takes approx. 5 minutes to administer.

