The research staff running the session will also periodically administer the Opioid Symptom Checklist (OSC). This questionnaire will be administered pre-drug administration, at the time of first drug administration, 1 hour post-drug administration, 2 hours post-drug administration, and 3 hours post-drug administration.

- **Opioid Symptom Checklist (OSC):** A 13-item scale used to quantify any sedation, somnolence, and other drug effects that the participant is experiencing from the buprenorphine and/or baclofen. Participants answer true/false questions about these opioid effects. This checklist takes approx. 2 minutes to administer.

Post-observation period

Once the 3-hour observation period has concluded, and the participant has finished all the QST tasks and questionnaires, they will be free to leave. Make sure they are not experiencing any severe side effects before allowing them to leave. If they are still feeling sick, allow them to wait a bit before leaving. Because we are giving them a drug known to produce somnolence as a side effect, participants will not be allowed to drive home and must have someone pick them up from their visit. If they are not able to have someone drive them home from the visit, we will arrange for an Uber Health taxi to bring them home (free of charge to the participant).

Post-visit procedures

Following the study visits, enter all data into REDCap that was recorded on paper forms. Also be sure that the urine drug screen and pregnancy test results are entered into REDCap. Update the participant tracking SPSS database (P:\[name]-Lab\BACUP\6. Databases → BACUP Participant Tracking).

Adverse event procedures

In the event that a participant has severe side effects from the study medication or procedures, the study doctor and PIs should be alerted as soon as possible. Examples of severe adverse side effects would be vomiting, blood pressure reading that is too high/too low, sudden spike or drop in body temperature, etc. If any of these occur, first alert one of the CRU nurses so that they can come check on the pt. Then, call the study doctor to let them

know what occurred. You can also have the CRU nurse talk to them so that they can relay treatment information to the nurse.

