Buprenorphine Plus Baclofen to Increase Analgesia in Healthy Volunteers

NCT04251819

November 14, 2025

Statistical Analysis Plan

All baseline characteristics and outcome measures were analyzed descriptively. Specifically, the means and standard deviations within each group (i.e., Placebo, Baclofen 5mg, and Baclofen 10mg) were calculated for all continuous variables. For the baseline characteristic of age, the mean and standard deviation of the overall sample was also calculated. For the categorical variables, frequencies of each category within each group and in the overall sample were calculated. No analyses were conducted to compare the groups on any variable.

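### Does dosing the two drugs 30 minutes apart in Group 2 spoil a study whose manual says procedures are identical across cohorts?

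*Protocol*

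**What the plan says.** Study session 2 of the Protocol defines two cohorts. The first (n=30) is "Randomized to either 5 mg of baclofen, 10 mg baclofen ,or 300 mcg of buprenorphine (n=10 per group"). The second (n=60) is "Randomized to 300 mcg of buprenorphine, and either: placebo, 5 mg of baclofen, or 10 mg of baclofen (n=20 per group"). The section then says "Following the administration of the study drug, all study procedures are identical for all groups and cohorts".

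The Visit timeline follows directly, with a separate schedule for each cohort: "The visit timeline for session 2 is as follows (represented below in 15-minute segments"). Group 1 takes its single drug at 0. Group 2 has one slot for buprenorphine and a later one for baclofen.

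The text gives these times after dosing:
- QST (Study session 2): "The QST tasks will be administered 1.5 hours post-drug administration".
- Mood and drug-effect surveys (Questionnaires): "at 30-45 minutes post-drug administration".
- Opioid Symptom Checklist, OSC (Questionnaires): before the drug, then "at the time of first drug administration, 1 hour post-drug administration, 2 hours post-drug administration, and 3 hours post-drug administration".

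None of these says which of the two drugs the interval is counted from in Group 2.

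The SAP describes a placebo group and two baclofen dose groups by means, standard deviations and frequencies, and adds: "No analyses were conducted to compare the groups on any variable".

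**The concern.** When two drugs are given at different times, a single interval after dosing can be true of only one of them. The sentence about identical procedures therefore seems to conflict with the timelines printed beneath it.

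The possible cost is to interpretation. According to Brief purpose of the study, Group 1 is there to show the effect of each drug on its own. Suppose buprenorphine alone is tested at one interval and buprenorphine with baclofen at another. Setting the two side by side would then mix the effect of baclofen with time since the opioid. The cohorts are also recruited one after the other, which adds calendar time. Finally, an unstated anchor could lead staff to time assessments, or the three-hour observation, from different doses.

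**Working it through.** **Inputs.** All come from the two session 2 timelines, at 15 minutes per column. Group 1 has 14 headers and 14 cells. Group 2 has 17 headers but only 13 readable cells, so 17 − 13 = 4 cells were lost when the table was extracted. I read the Group 2 cells from the left and then test that reading.

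**Group 1.** Drug at 0, QST at 1 h 30: 90 − 0 = 90 minutes. This reproduces the stated 1.5 hours.

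**Group 2.** Buprenorphine is in the 15-minute column and baclofen in the 45-minute column, so the doses are 45 − 15 = 30 minutes apart. Minutes after each drug are column time − 15 and column time − 45:

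| Event | Group 1, after its drug | Group 2 column | After buprenorphine | After baclofen | Text |
|---|---|---|---|---|---|
| First blood draw | 30 | 75 | 60 | 30 | none given |
| Surveys | 30 | 90 | 75 | 45 | 30–45 |
| First OSC after dosing | 60 | 105 | 90 | 60 | 60 |
| QST | 90 | 135 | 120 | 90 | 90 |
| Next OSC | 120 | 165 | 150 | 120 | 120 |

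Counted from baclofen, every row with a stated time agrees with the text. Counted from buprenorphine, none does. The OSC tied to the first drug is a separate time point and matches the Group 2 cell that pairs buprenorphine administration with an OSC. It does not conflict with a later clock that runs from baclofen.

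**Do the lost cells matter?** Buprenorphine is the 2nd readable cell and QST the 10th, so they are at least (10 − 2) × 15 = 120 minutes apart. If all four lost cells lay between them, the interval would be 12 × 15 = 180. Over every order-preserving placement it is 120 to 180 minutes, never 90. Buprenorphine to baclofen is at least (4 − 2) × 15 = 30 minutes. The mismatch is therefore not an extraction artefact. The agreement with the text in the table depends on reading from the left, and the agreement itself supports that reading.

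**Could a different anchor remove the mismatch?** No. With doses 30 minutes apart, time since buprenorphine always equals time since baclofen plus 30. If QST were fixed at 90 minutes after buprenorphine, it would fall 90 − 30 = 60 minutes after baclofen, and the 20 baclofen-alone participants would be the ones out of step. As printed, those 20 match Group 2 at 90 minutes, and the 10 on buprenorphine alone do not (90 against 120).

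**What could not be checked.** The row marking the start and end of observation has lost its column positions. Three hours would end at 0:15 + 3:00 = 3:15 or at 0:45 + 3:00 = 3:45, depending on the dose counted. The readable text does not show which was meant, so it cannot be called contradictory. No readable Group 2 cell shows the second blood draw.

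**The case for a change.** The best case for acting is that the manual treats timing as important. Pain tasks (QST) explains the 1.5-hour interval as chosen to catch the drugs at full effect, so 120 minutes against 90 is not trivial on the authors' own terms. The SAP does not name the cohort behind its groups, and both cohorts contain 5 mg and 10 mg baclofen arms, so a reader might set them side by side. Stating the anchor would take only a few words.

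Part of this stands. The anchor is missing, the word identical is loose, and the interval after buprenorphine does differ for the Group 1 buprenorphine arm. Anyone who later shows that arm beside Group 2 should say so.

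The rest does not carry. The sentence speaks of procedures, and two openly different schedules sit directly below it. Its natural meaning is the same tasks, and the difference in timing is disclosed. No section plans a contrast between cohorts, pooling, or a test of additivity. The SAP's group labels include placebo, which only the second cohort has, so they point to Group 2. A rule naming a reference arm or barring pooling would govern analyses that do not exist. Reporting actual minutes from each dose to QST assumes those times were recorded. The documents mention a recorded time only for blood collection at visit 1. Sequential recruitment is a separate matter that the dosing clock would not change.

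**Conclusion.** No change to the plan follows. The gap is an unstated anchor that the timeline itself lets a reader infer. The resulting mismatch is 30 minutes in the buprenorphine-to-QST interval, for 10 of 30 + 60 = 90 planned participants. Whether baclofen adds to buprenorphine is addressed within the 60 randomized Group 2 participants, whose three arms share one printed schedule, so the stagger is common to all of them. The SAP makes no comparison that the mismatch could bias. Its past tense suggests that the data were already collected, in which case new wording could not alter them.

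This rests on three assumptions: the Group 2 cells are read from the left, placebo is given in the baclofen slot (the manual does not say so), and no comparison between cohorts is intended. If the third failed, the 90 against 120 minutes would need to be stated beside any such result. Reconciling the wording of the manual's timing sections is a clerical matter for the study team. Which dosing or observation schedule is right is not judged here.
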